### **8.3 Other Objectives**

For patients for whom any MRI data are available:

- To evaluate MS-related lesions as assessed by MRI in patients with HDA-RRMS after cladribine tablet initiation

## 9 Research Methods

### 9.1 Study Design

#### 9.1.1 Design Overview

This will be a multicentre chart review, Phase IV study, to be conducted across approximately 7 or 8 sites in the UK, using medical records of patients who initiated cladribine tablet monotherapy for treatment of HDA-RRMS per clinical practice. The observational chart review study design, allowing collection of real-world data dating back to product launch, will maximise the patient observation periods while minimising the burden for the sites and patients.

Patients with HDA-RRMS who initiated treatment with cladribine tablets and are fulfilling the other study eligibility criteria will be identified from patient records and asked to consent to participate in the study. Informed consent may be obtained at the site or remotely (additional details are provided in [Section 10.1](#)). Patients should have initiated treatment with cladribine tablets between 22 August 2017 (i.e., date of EU marketing authorisation of cladribine tablets) and at least 3 years before enrolling into the study. In addition, the patient should have completed at least Year 1 of cladribine treatment (i.e., 2 treatment weeks). Sites should aim to enrol patients in chronological order, based on the start date of treatment with cladribine tablets: i.e., patients who initiated cladribine tablets first will be contacted for enrolment first and their data should be abstracted first.

In this observational chart review study, the drug was prescribed before the patient was enrolled in the study as part of routine clinical practice and independent from participation in the current study.

[figure not shown]
The enrolment date is defined as the date of signing informed consent. Annual chart reviews will be based upon the date of cladribine tablet initiation, which is defined as the start date of Year 1 treatment with cladribine tablets as documented in patients' medical records. This study will involve 2 chart abstractions, with the first chart abstraction at the patient's enrolment and the second chart abstraction approximately 1 year after enrolment ([Figure 1](#)).

The first chart review will take place after obtaining patients' consent to participate in this study. Patient data will be abstracted within 28 days after obtaining informed consent. The data will be abstracted from the medical chart and will include relevant medical history, data recorded in the year prior to cladribine tablet initiation, and data recorded between the date of treatment initiation with cladribine tablets and the study enrolment date ([Table 1](#) and [Section 9.3](#)). In addition, the patient's general practitioner may be contacted by the principal investigator or a member of the site team to obtain information regarding medical history and concomitant medications.

The second chart review will be conducted approximately 1 year after enrolment (within a window of 14 days from a year after the enrolment date). This second chart abstraction will collect data recorded between the enrolment date and the date of the second data abstraction ([Table 1](#) and [Section 9.3](#)).

The data to be collected are routinely collected information per clinical practice, including demographic data, disease characteristics (relapse reports, Expanded Disease Severity Scale [EDSS] scores, MRIs, and lymphocyte counts, as available), treatments (cladribine tablets, other DMTs for MS, and COVID-19 vaccines), medical history, and selected AEs.

**Figure 1** **Study Design Schematic**

ICF: Informed Consent Form

### 9.1.2 Outcomes

The primary and secondary outcomes will be analysed overall and stratified by most recent prior DMT subgroups:

- naïve to DMT
- prior platform therapy
- prior high-efficacy cell-depleting treatment
- prior high-efficacy non-depleting treatment

#### 9.1.2.1 Primary

- Estimated annualised relapse rate in the year prior to treatment initiation with cladribine tablets, and in years 1, 2, 3, 4 and 5 after initiation

The annualised relapse rate will be calculated from the number of clinician's confirmed relapses that occurred over the respective year.

### 9.1.2.2 Secondary

- Proportion of patients who remain relapse-free in each year and at 4 and 5 years after initiation of cladribine tablet treatment
- Time from cladribine tablet initiation to first relapse
- Proportion of patients who discontinued cladribine tablets and reasons for discontinuation
- Subsequent DMTs (none or by DMT type) received after cladribine tablets discontinuation/treatment completion up to 5 years after cladribine tablets initiation
- Disability assessed by the EDSS at treatment initiation and start of treatment Year 2

The EDSS is a neurological assessment to evaluate disability in patients with MS, performed by the physician. The annual EDSS at cladribine tablet treatment initiation and start of treatment Year 2 will be recorded, where available in the patients' notes. EDSS is routinely collected as part of standard care in the UK as part of the annual assessment required for continuation of treatment.

- Proportion of patients with disability progression confirmed over 6 months, assessed by the EDSS, at 2 years after cladribine tablet treatment initiation

An EDSS progression is defined as an increase in the EDSS scale as follows:

- If the EDSS score at cladribine tablet initiation is 0, the increase must be  $\geq 1.5$  units
- If the EDSS score at cladribine tablet initiation is  $\geq 0.5$  or  $\leq 4.5$ , the increase must be  $\geq 1.0$  units
- If the EDSS score at cladribine tablet initiation is  $\geq 5.0$ , the increase must be  $\geq 0.5$  units.

A confirmed disability progression is defined as EDSS progression (as defined above) confirmed after 6 months.

- Rates of selected, identified, and potentially clinically important AEs, including:

- grade 3 lymphopenia
- grade 4 lymphopenia
- herpes infections
- serious infections (infections for which a hospitalisation is initiated or extended)
- opportunistic infections (new onset or reactivation of latent infection)
- malignancies

These AEs will be reported from the date of cladribine tablet initiation and will be described overall and by most recent prior DMT subgroups (DMT naïve, prior platform treatment, prior high-efficacy cell-depleting treatment, and prior high-efficacy non-depleting treatment).

### **9.1.2.3                    Others**

For patients for whom any MRI data are available:

- Number of MRI lesions: T1 gadolinium enhancing lesions, T2 lesions (new/enlarging compared to a previous scan)

MRI measures of white matter lesional activity (i.e., new/enlarging T2 lesions, T1 hypointense or Gd-enhancing T1 lesions) have shown to be valid surrogate endpoints for clinical outcomes of disease progression ([Wattjes MP 2015](#)).

## **9.2                            Setting**

### **9.2.1                            Study Population**

The study population will be recruited from approximately 7 or 8 sites in the UK and will be identified according to the inclusion and exclusion criteria listed below.

#### **9.2.1.1                            Inclusion Criteria**

For inclusion in the study, all of the following inclusion criteria must be fulfilled:

1. At least 18 years of age at cladribine tablet treatment initiation
2. Physician diagnosis of HDA-RRMS as defined by clinical or radiological features
3. Treatment initiation with cladribine tablet monotherapy on or after 22 August 2017 and at least 3 years before enrolment
4. Completion of Year 1 treatment of cladribine tablets (Week 1 and Week 2 treatment, per recommended dose in Year 1: 1.75 mg/kg body weight, cumulatively)
5. Provide written informed consent to participate in the study

#### **9.2.1.2                            Exclusion Criteria**

Patients are not eligible for this study if they fulfil any of the following exclusion criteria:

1. Received cladribine tablet treatment within an interventional clinical trial during the study period
2. Received treatment with any investigational therapy for RRMS in the 6 months prior to cladribine tablet treatment initiation

## 9.2.2 Definition of Study Cohorts and Description of Treatments

This is a multicentre chart review study enrolling subjects with HDA-RRMS, who completed at least Year 1 treatment with cladribine tablets in routine clinical practice following the SmPC.

According to the EU SmPC, each treatment year consists of 2 treatment weeks, 1 at the beginning of the first month and 1 at the beginning of the second month of the respective treatment year. Each treatment week consists of 4 or 5 days on which a subject receives 10 mg or 20 mg (1 or 2 tablets) as a single daily dose, depending on body weight. If necessary, the treatment course in Year 2 can be delayed for up to 6 months (18 months after initiation) to allow for recovery of lymphocytes (at least 800 cells/mm^3). If this recovery takes more than 6 months, the subject should not receive cladribine tablets anymore.

## 9.2.3 Observation Period

The total observation period per patient will vary, depending on the pre-enrolment time on cladribine tablet treatment (i.e., the period between the date of cladribine tablet initiation and study enrolment date). The observation period per patient, counting from 1 year prior to cladribine tablet initiation until the date of the second chart review, will be at minimum 5 years and at maximum 7 years.

## 9.2.4 Overview of Study Events

An overview of the planned study events and data collection are provided in [Table 1](#).

At enrolment (i.e., date of signing informed consent form [ICF]), the first chart review should be performed within the following 28 calendar days. The second chart review should be approximately 1 year from enrolment (365 calendar days ± 14 calendar days).

The data have been collected per routine practice at the discretion of the treating physician. In addition, the patient's general practitioner may be contacted by the principal investigator or a member of the site team to obtain information regarding medical history and concomitant medications. All data will be collected upon availability.

**Table 1 Schedule of Study Events**

Data	Enrolment (Day 1)	Chart Review 1 (Day 1)	Chart Review 2 (Year 1)
Window	-	+28 days	±14 days
Informed consent	X		
Eligibility criteria		X	
Demographic data		X	
Medical history and comorbidities		X	
Medication history		X	
MS disease history		X	

Data	Enrolment (Day 1)	Chart Review 1 (Day 1)	Chart Review 2 (Year 1)
Prior disease-modifying therapies		X	
Treatment with cladribine tablets		X	
Subsequent disease-modifying therapies		X	X
COVID-19 vaccines		X	X
Clinical confirmed relapses		X	X
Annual EDSS scores		X	X
MRI data		X	X
Lymphocyte levels		X	X
Selected adverse events		X	X

EDSS: Expanded Disability Status Scale; MRI: Magnetic Resonance Imaging; MS: Multiple Sclerosis

## **9.2.5 Withdrawal from the Study**

Patients are free to discontinue the study at any time without giving their reasons. In addition, patients can be withdrawn from the study for the following reason:

- Enrolment in an investigational clinical trial during the study period

## **9.3 Variables**

- Demographic data at cladribine tablet initiation: Gender, age, height and weight measurements on or nearest to the date of initiating cladribine tablets in the year prior to treatment initiation
- Medical history and comorbidities at cladribine tablet initiation: All relevant medical history and comorbidities in the year prior to initiation with cladribine tablets (both past and ongoing comorbidities at date of initiation with cladribine tablets will be collected)
- Medication history at cladribine tablet initiation: Relevant medications taken in the year prior to initiation with cladribine tablets
- MS disease history: Date of initial MS diagnosis and type of MS at cladribine tablet initiation
- Prior DMTs: Any DMT for MS, taken since initial MS diagnosis and prior to initiating treatment with cladribine tablets, including starting date, end date, and dosage. The most recent DMT taken prior to initiation with cladribine tablets will be categorised in subgroups, as defined in [Section 9.7.1.1](#):
  - naïve to DMT
  - prior platform therapy
  - prior high-efficacy cell-depleting treatment

- prior high-efficacy non-depleting treatment
- Treatment with cladribine tablets: date of initiation of each treatment course, dose, potential date of discontinuation of treatment and reason for discontinuation, if applicable.
- Subsequent DMTs: Other DMTs for MS initiated after treatment with cladribine tablets will be recorded, including the date of initiation, potential discontinuation date, and dosage.
- COVID-19 vaccines: Vaccines for coronavirus disease 2019 (COVID-19) attributable to severe acute respiratory syndrome coronavirus 2 (SARS-CoV-2) administered in the years after initiation of cladribine tablets (until end of observation period) will be recorded.
- Course of disease:
  - clinician confirmed relapses: Each relapse that occurred in the year prior to treatment initiation with cladribine tablets and each year after will be recorded with the onset date (at least month and year)
  - annual EDSS scores: At start of cladribine tablet treatment Year 1, at the start of cladribine tablet treatment Year 2, and 2 years after cladribine tablet treatment initiation
  - MRI data (upon availability): T1 gadolinium enhancing lesions, T2 lesions (new/enlarging compared to a previous scan)
- Lymphocyte levels: At initiation of cladribine tablet treatment and during the years after, where available.
- Selected adverse events: Reporting of AEs once informed consent has been obtained (as described in [Section 11](#)), with special focus on:
  - grade 3 lymphopenia
  - grade 4 lymphopenia
  - herpes infections
  - serious infections (infections for which a hospitalisation is initiated or extended), opportunistic infections (new onset or reactivation of latent infection)
  - malignancies.

For each AE, the start date, end date, classification of serious or non-serious, and outcome should be reported.

Derived and transformed data needed for the analysis are described in [Section 9.7.2](#).

## 9.4 Data Source

Data for this study will be abstracted from patients' medical records. The investigator or appropriately delegated personnel will transcribe data from medical records into an electronic case

---

report form (eCRF). In addition, the patient's general practitioner may be contacted by the principal investigator or a member of the site team to obtain information regarding medical history and concomitant medications. The data in the eCRF should be consistent with the relevant source documents. Site staff will be entering data.

Data collected from the patient's medical records will include demographics, MRI scan reports, medical and medication history, comorbidities, cladribine tablet treatment, concomitant medications, and AEs. All data will be reviewed and potentially queried for clarifications and/or corrections of inconsistent or missing data. Further details are provided in [Section 9.6](#).

## **9.5 Study Size**

Approximately 200 patients will be enrolled in this study, with a minimum of 90 patients. This sample size is based on an estimation of what is feasible during the study period. The study will not be powered to detect or report statistical differences and has no comparator group. It will be qualitative and descriptive in nature.

With an expected annualised relapse rate of 0.14 over 2 years ([Giovannoni 2010](#)), the distance from proportion to limit of the corresponding 95% confidence interval (CI) will be 0.072 based on available data for 90 patients.

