### 9.7.3 Statistical Methods

No formal statistical hypothesis will be tested, given the descriptive nature of the study.

Descriptive statistics will be used to summarize data. Quantitative (continuous) variables will be summarised using descriptive statistics, i.e., the number of patients with non-missing value, the number of patients with missing value, the mean, SD, median, minimum, and maximum, and first and third quartile. Qualitative (categorical) variables will be displayed as frequency counts and percentages (n, %).

If CIs are to be calculated, these will be 2-sided with a confidence probability of 95%, unless otherwise specified. For continuous data, CIs for the mean will be calculated assuming a normal distribution of the data. The CIs for binary outcomes will be presented using the Clopper-Pearson method.

The primary, secondary, and other analyses will be performed on the FAS.

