#### Primary Outcome Analysis

The annualised relapse rate for a patient is defined as the number of clinician's confirmed relapses that occurred in the year prior to the date of cladribine tablet initiation, and in Years 1, 2, 3, 4 and 5 after treatment initiation with cladribine tablets (upon availability, depending on the available observation time):

- Year prior to date of cladribine tablet initiation: Month -12 to the day before the date of cladribine tablet initiation (Start Month 1)
- Year 1: Start Month 1 to End of Month 12
- Year 2: Start Month 13 to End of Month 24
- Year 3: Start Month 25 to End of Month 36
- Year 4: Start Month 37 to End of Month 48
- Year 5: Start Month 49 to End of Month 60

Relapses will be counted for the defined time period if the date of onset of the relapse is within the defined time period. In the analyses defined in the IAP, an "induction period" after treatment initiation may be considered for the annualised relapse rate in Year 1.

The annualised relapse rate for a patient will be calculated by dividing the number of clinician confirmed relapses during the period by the person-years of the patient (i.e., the period [in days] that a patient was observed in the study divided by 365.25).

The estimated annualised relapse rate in each of the defined years above will be summarised using descriptive statistics for continuous variables.

The annualised relapse rate will be described overall and among the subgroups by most recent prior DMT, as defined in [Table 2](#).

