- Number of tablets taken per week of ‘Year 1’, ‘Year 2’ and each subsequent course of cladribine
- Total number of tablets taken on ‘Year 1’, ‘Year 2’ and each subsequent course of cladribine
- Cumulative number of tablets taken (cumulative over Year 1 and Year 2, and cumulative over all courses of cladribine treatment)
- Number % of patients with no dose and dose delayed (with the corresponding reasons)
- Number % of patients with a complete course of cladribine at ‘Year 1’, ‘Year 2’, any additional courses of cladribine treatment and overall

14 Effectiveness

The following analyses will be performed based on the FAS by the most recent prior DMT and overall.

14.1 *Primary Outcome: ARR*

14.1.1 *Primary Objective: Derivation and analysis of the primary outcome: ARR*

The annualised relapse rate (ARR) will be derived from the 'Clinical Confirmed Relapses' CRF page.

The relapses observed will be assigned for the calculation for the ARR as indicated on [Table 1](#) in Section 9.6.

The ARR for a patient will be calculated by dividing the number of clinicians confirmed relapses observed within each period (Year) by the person-years of the patient in the period.

The person-years for a patient will be assigned as follows:

- $(365.25-84)/365.25$ years for time-point 'Year 1' for the full effectiveness period (main analysis)
- $(365.25-56)/365.25$ years for time-point 'Year 1' for the amplified effectiveness period (sensitivity analysis #1)
- 1 year for time-point 'Year 1' for the full treatment effectiveness period (sensitivity analysis #2)

And 1 year for each other interval (-1, 2, 3, 4, 5) unless the date of last contact occurs within that interval. In this case that interval person-years will be calculated until the date of last contact. The patient will not contribute to the ARR calculation for the following intervals (if any).

The 95% confidence interval (CI) will be calculated using the exact Poisson method.

14.2 *Secondary Outcomes*

14.2.1 *Secondary Objective: Derivation and analysis of the secondary outcome: RFR*

The relapse-free rate (RFR) is defined as the time from the on-treatment period start date (see [Table 3](#)) until the date of the first relapse or death as assessed by the investigator:

- RFR (years): $(\text{First relapse date or death or date of censoring} - \text{on-treatment start date} + 1) / 365.25$.

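### The 0.072 precision quoted for 90 patients is a binomial half-width; the planned exact Poisson interval for a yearly relapse rate of 0.14 is wider (half-width 0.084, or 0.097 in Year 1)

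*Protocol*

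**What the plan says.** Protocol 9.5 sets the size by feasibility: "Approximately 200 patients will be enrolled in this study, with a minimum of 90 patients". It then gives one precision statement. It begins "With an expected annualised relapse rate of 0.14 over 2 years" and concludes that "the distance from proportion to limit of the corresponding 95% confidence interval (CI) will be 0.072 based on available data for 90 patients".

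The primary outcome analysis in Protocol 9.7.3 defines the patient-level rate, separately for each year, by "dividing the number of clinician confirmed relapses during the period by the person-years of the patient". The general rules in 9.7.3 say of any confidence intervals that "these will be 2-sided with a confidence probability of 95%, unless otherwise specified", and add: "For continuous data, CIs for the mean will be calculated assuming a normal distribution of the data".

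SAP 14.1.1 fixes the interval for the relapse rate: "The 95% confidence interval (CI) will be calculated using the exact Poisson method". It credits each patient with (365.25 − 84)/365.25 person-years in the Year 1 main analysis and with one person-year in each other interval, unless last contact falls inside it. SAP 7 reports no changes from the protocol's planned analyses, and neither document restates the precision for the Poisson interval.

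**The concern.** A relapse rate is not a proportion. A patient can relapse more than once in a year, and the denominator is person-time, not a count of patients. The binomial variance p(1 − p)/n therefore does not apply, and it is smaller than the Poisson variance for the same value, 0.14. The word proportion in 9.5 suggests that a binomial formula was used.

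The study is descriptive, so interval width is the main quantitative statement of what a given size delivers. The figure is given for the minimum size, where it matters most. A reader would take it to mean an upper limit near 0.14 + 0.072 = 0.21 at 90 patients. The question is how far the planned method departs from that.

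**Working it through.** **Inputs.** Rate 0.14 and 90 patients (target about 200): Protocol 9.5. Two-sided 95%: Protocol 9.7.3. Exact Poisson method and Year 1 person-time: SAP 14.1.1.

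**Reproducing the stated figure.** Binomial, normal approximation: 1.96 × √(0.14 × 0.86/90) = 0.0717, which rounds to 0.072. A Wilson interval also has half-width 0.0717. The Poisson alternatives do not give 0.072:

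- Normal approximation, 90 person-years: 1.96 × √(0.14/90) = 0.0773
- Normal approximation, 180 person-years (two years pooled): 1.96 × √(0.14/180) = 0.0547
- Exact, 180 person-years: half-width 0.058

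**Person-time under the plan.** Year 1 main analysis: 281.25/365.25 = 0.770 person-years per patient, so 90 × 0.770 = 69.3 and 200 × 0.770 = 154.0. Any other complete year: 90 and 200.

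**Exact Poisson limits.** With T person-years and expected count m = 0.14 × T:

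- lower = χ²(0.025; 2m)/(2T)
- upper = χ²(0.975; 2m + 2)/(2T)
- half-width = (upper − lower)/2

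For example, at T = 90, m = 12.6: lower = 13.264/180 = 0.0737 and upper = 43.448/180 = 0.2414.

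| Patients | Period | T | m | 95% CI | Below | Above | Half-width |
|---|---|---|---|---|---|---|---|
| 90 | Full year | 90 | 12.6 | 0.074 to 0.241 | 0.066 | 0.101 | 0.084 |
| 90 | Year 1 main | 69.3 | 9.70 | 0.066 to 0.260 | 0.074 | 0.120 | 0.097 |
| 200 | Full year | 200 | 28.0 | 0.093 to 0.202 | 0.047 | 0.062 | 0.055 |
| 200 | Year 1 main | 154.0 | 21.56 | 0.087 to 0.213 | 0.053 | 0.073 | 0.063 |

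Against 0.072, the half-widths at 90 patients are larger by 0.0838/0.072 = 1.16 and 0.0968/0.072 = 1.34.

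**Check with whole counts.** The expected counts at 90 patients are not integers. Twelve or 13 relapses in 90 person-years give half-widths of 0.082 and 0.085; 9 or 10 in 69.3 person-years give 0.094 and 0.098. The conclusion is the same.

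**Where the increase comes from.** Like for like on the normal approximation, moving from binomial to Poisson gives 0.0773/0.0717 = 1.08, about 8%. The rest of the full-year increase comes from the exact method. Year 1 also has less person-time.

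**Size at which 0.072 holds.** The exact half-width reaches 0.072 at 119.2 person-years: about 120 patients for a full year, or 119.2/0.770 = 154.9, about 155, for the Year 1 main analysis.

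**The case against.** The strongest reply is that little depends on the figure. Protocol 9.5 bases the size on feasibility and disclaims power, 9.7.3 states that no hypothesis is tested, and no precision target or decision rule is tied to 0.072. That stands, and it limits the point to a correction of one sentence.

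The sum itself is right for its formula; the fault is that the formula does not match the outcome or the planned interval. Planning with a normal approximation and analysing with an exact method is ordinary practice, and on that basis the understatement is only about 8%. This also stands. But 9.5 describes the interval that will be reported, and that interval is the exact one.

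The text speaks of the distance to a limit, and half the width of an asymmetric interval is not the distance to either limit. This is fair: for a full year the lower distance (0.066) is better than stated and only the upper (0.101) is worse. For Year 1 both exceed 0.072 (0.074 and 0.120).

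The 0.14 is described as a rate over 2 years, so pooling might have been meant. Pooling gives 0.055 to 0.058, which does not reproduce 0.072, and the plan contains no pooled 2-year estimate.

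Finally, SAP 14.1.1 defines the rate per patient and does not spell out that the Poisson interval uses total relapses over total person-years. That is the natural reading and the one used here, but it is an assumption.

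**Conclusion.** The concern holds. The 0.072 in Protocol 9.5 is a binomial figure attached to a rate, and the interval planned in SAP 14.1.1 does not deliver it at 90 patients. The planned upper limit is about 0.24 for a full year and 0.26 for the Year 1 main analysis, not about 0.21. At about 200 patients the half-width is below 0.072 in both cases; the Year 1 upper distance of 0.073 essentially meets it.

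These figures assume a rate of 0.14 in every period (including days 84 to 365 of Year 1), pooled relapses over pooled person-years, complete person-time and no overdispersion. The last two are favourable. Protocol 9.2.3 allows a minimum of 5 years of observation including the year before initiation, so some patients may have only about 4 years afterwards. Ninety patients need not give 90 person-years in Year 5, where the interval could be wider still.

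The consequence is modest: no estimate, test or sample size changes. The figure should still be corrected, because it is the only precision statement in 9.5 and it overstates what the minimum size achieves.

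**What to change.** Replace the last sentence of Protocol 9.5 with, for example:

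> With an annualised relapse rate of 0.14, the exact Poisson 95% CI for a full year would be about 0.07 to 0.24 with 90 patients and about 0.09 to 0.20 with 200 patients. For the Year 1 main analysis, which excludes the 84-day induction period, it would be about 0.07 to 0.26 with 90 patients and about 0.09 to 0.21 with 200 patients. These figures assume complete person-time and no overdispersion; fewer person-years are expected in Year 5.

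This also removes the word proportion. If the protocol will not be amended again, the same text can go in the SAP or the study report.

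The cost is wording only. The stated precision at 90 patients becomes less favourable; the sample size, the estimate and the interval method stay as they are.
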